3.2 Study design

A two-phase historical cross-sectional and cohort study using routine electronic patient records from UK primary care practices. The study period will be 2010-2017 (or the latest available data). It will include patients with active asthma. In Phase 1 the frequency of each combination of comorbidities will be estimated using most recent clinical data available for each eligible patient. In Phase 2, the clinical characteristics and service use in a 1-year period after the date of co-morbidity assessment will be described for a pre-selected set of common comorbidity clusters.

[figure not shown]

Figure 1: Study design Phase 2

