4.2 Inclusion and exclusion criteria

Inclusion criteria

Registered at a participating practice for at least one year prior to their index date and within the study period. In phase 1, the cross-sectional assessment of co-morbidity co-occurrence, the index date for each patient will be the earlier of the following dates: the last data collection from each practice and 6 months before patient deregistration (to avoid gaps in the clinical data due to late recording of patient deregistrations). For CPRD practices with linked HES data, the index date will be the earliest of the following dates: the last data collection from each practice, 6 months before patient deregistration, date of last HES record. In phase 2, the index date will be one year before the last data collection from each practice and 6 months before patient deregistration, to allow for one year of follow-up.

Patient had active asthma at their index date:

- a diagnosis of asthma at any time before their index date (using QOF Read codes: see Appendix 1); AND
- two or more prescriptions for an asthma medication in the preceding year.

Exclusion criteria

Any other chronic lower respiratory condition recorded at any time (Read coded: see Appendix 2). These are:

- Lung disease due to external agents, other than smoking, such as occupational agents.
- Active COPD (a Read code at any time + medication in the last year of follow-up).
- Bronchiolitis obliterans.
- Pulmonary fibrosis.
- Pulmonary hypertension.
- Cystic fibrosis

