5.4 Quantifying health resource use (HRU) and costs

The following HRU outcomes and associated costs will be tabulated for each of the comorbidity clusters identified in phase 1. These will be for the year prior to the index date. Secondary care resource use and costs will be limited to patients with linked secondary care (HES) data and the most recent HES year. Costs will be reported in 2017 GB pounds.

Primary care

1. Physician office visits:
 - a. Number and cost of asthma-related consultations.
2. Number of primary care medication prescriptions:
 - a. ICS
 - b. ICS/LABA
 - c. SABA
 - d. SAMA
 - e. LABA
 - f. LAMA
 - g. LABA/LAMA
 - h. LTRA
 - i. biologics (where known)
 - j. chronic oral corticosteroids
 - k. antibiotics
3. Total cost of asthma drug prescribing.
4. Total cost of oral corticosteroid and antibiotic prescribing.
5. Total primary care costs (physician office visits + prescribing).

Secondary care

6. Outpatient visits:
 - a. Number and cost of asthma-related outpatient visits.
7. Emergency Room attendances:
 - a. Number and cost of asthma-related Emergency Room attendances.
8. Inpatient hospital admissions:
 - a. Number and cost of asthma-related hospital admissions.
9. Total secondary care costs (outpatient + ER + inpatient).

Combined primary and secondary HRU and costs

11. Total primary and secondary care costs (primary care + secondary care).

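### In Phase 2 the COPD exclusion is decided by prescriptions issued after the index date, so cohort membership rests on post-index records and, under section 3.2, on part of the outcome year

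*Protocol*

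**What the plan says.** Protocol section 4.2 ties entry to the index date: active asthma needs "a diagnosis of asthma at any time before their index date" plus at least two asthma prescriptions in the year before it. The exclusions, one list for both phases, have no such anchor. The general rule covers "Any other chronic lower respiratory condition recorded at any time", and the COPD item reads "Active COPD (a Read code at any time + medication in the last year of follow-up").

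The index date differs by phase. In Phase 1 it is the earlier of "the last data collection from each practice and 6 months before patient deregistration". For Phase 2 the text reads "In phase 2, the index date will be one year before the last data collection from each practice and 6 months before patient deregistration", with the stated purpose "to allow for one year of follow-up".

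Section 3.2 says Phase 2 will describe "service use in a 1-year period after the date of co-morbidity assessment". Section 5.4 lists the resource-use outcomes, among them "Number of primary care medication prescriptions" by drug class and the matching costs, but sections 5.4 and 6.7 both place them in the year before the index date.

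**The concern.** A cohort defined at an index date should be identifiable from what is known on that date. Here the inclusion criteria meet that test and the COPD exclusion does not. Two patients with the same COPD code and the same active asthma at index can be treated differently only because one received a qualifying prescription in the following year and the other did not.

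If that year is also when service use is measured, the rule conditions the cohort on something close to the outcome. Mean prescribing and cost could be shifted. The contrast between comorbidity clusters could also be shifted if COPD codes are more common in some clusters than in others, for example in those with an older age mix. Covariate adjustment under section 6.8 does not undo selection on a post-index event.

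**Working it through.** **1. Place the windows on a month scale.** Take last data collection as month 0 and a patient still registered then. The inputs are the index-date and exclusion rules in section 4.2.

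| | Index date | Last year of follow-up | Months of that year after index |
|---|---|---|---|
| Phase 1 | 0 | -12 to 0 | 0 of 12 |
| Phase 2 | -12 | -12 to 0 | 12 of 12 |

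The same words give a pre-index window in Phase 1 and a post-index window in Phase 2. The wording fits Phase 1 and appears to have been carried over when the index date moved.

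For a patient who left the practice, the Phase 2 index sentence can be read in two ways. If index is 6 months before deregistration and follow-up runs to deregistration, 12 - 6 = 6 of the 12 months fall before index and 6 after. If index is a further year back (18 months before deregistration), the whole last year falls after index. Some post-index prescribing decides membership either way.

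**2. Set the outcome windows beside it.**
- Section 3.2: the year after comorbidity assessment, months -12 to 0 in Phase 2. It coincides with the COPD medication window.
- Sections 5.4 and 6.7: the year before index, months -24 to -12. There is no overlap with the medication window.
- Section 5.1: GINA step and risk-domain control use the year before index, and overall control uses the baseline year. Section 5.3 assesses comorbidity activity and severity at index, from earlier records. None uses the follow-up year.

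**3. Size, by assumption only.** The protocol gives no COPD prevalence, no share coded after index and no cost for such patients.

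(a) *Patients kept because no qualifying prescription followed.* Let f be the share of otherwise eligible patients with a COPD code and z the share of those without qualifying medication in the post-index year. Their share of the retained cohort is f·z / (1 - f + f·z).
- f = 5%, z = 3%: 0.0015 / 0.9515 = 0.16%.
- f = 15%, z = 10%: 0.015 / 0.865 = 1.73%.

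(b) *Patients removed only because of post-index records, under any of the exclusions.* Let q be their share of the index-date cohort and r their mean follow-up cost relative to retained patients. Mean cost is understated by 1 - 1/(1 + q(r - 1)).
- q = 0.5%, r = 2: 1 - 1/1.005 = 0.50%.
- q = 1%, r = 3: 1 - 1/1.02 = 1.96%.
- q = 3%, r = 3: 1 - 1/1.06 = 5.66%.
- q = 5%, r = 4: 1 - 1/1.15 = 13.04% (a stress value).

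(c) *Contrast between two clusters A and B.* If their retained means are equal, the ratio before removal is (1 + q_B(r - 1)) / (1 + q_A(r - 1)).
- q_A = 1%, q_B = 5%, r = 2: 1.05 / 1.01 = 1.040.
- q_A = 1%, q_B = 5%, r = 4: 1.15 / 1.03 = 1.117.
- q_A = q_B = 3%, same r: 1.000.

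The contrast is affected only if removal, or the relative cost of those removed, differs between clusters. Parts (b) and (c) apply to cost measured after index, as in section 3.2.

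**4. Check the obvious remedy.** Every eligible patient already has at least two asthma prescriptions in the year before index. If asthma drugs count as COPD medication, moving the window to that year excludes every patient with a prior COPD code. The list of qualifying drugs therefore has to be settled together with the window.

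**The case against.** The best defence has four parts.

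*The outcome year is disputed.* Sections 5.4 and 6.7 put resource use before index, and only section 3.2 looks forward. This stands: selection on the resource-use outcome is conditional on how that conflict is resolved. It does not rescue the rule, because membership would still depend on records made after index.

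*Follow-up is not defined.* The phrase may mean the last year of available record, as it must in Phase 1, and the Phase 2 design figure is not reproduced in the text at hand. But the last year of record in Phase 2 is the post-index year for a patient registered to the end, and section 4.2 itself uses the word follow-up for that year.

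*Excluding on a diagnosis at any time can be deliberate.* A later code for pulmonary fibrosis or cystic fibrosis may show that earlier respiratory records were not simple asthma. This stands as a reasonable trade-off for the other listed conditions, although the protocol gives no such reason and its only sensitivity analysis (section 6.9) concerns record length. It does not justify the COPD medication window: a prescription in the following year does not show whether the asthma label was right.

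*The effect is small and its size is assumed.* This also stands.

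A reader might infer more: that COPD-coded patients who remain are zero users by construction, or that severity comparisons are distorted. The documents do not support either. The qualifying medications are not listed, so overlap with the outcome drug classes is likely but not stated. On the 5.4 and 6.7 reading, every retained patient has at least two asthma prescriptions in the outcome year. The severity measures with a stated window are pre-index.

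**Conclusion.** The point holds for the COPD medication window. In Phase 2 it lies after the index date, for all 12 months in a patient registered to the end of data collection, so post-index prescribing decides who is in the cohort. Under section 3.2 this selects on part of the outcome; under sections 5.4 and 6.7 it does not overlap resource use but remains an exclusion that cannot be applied at index.

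The size cannot be derived from the documents. With q of 0.5% to 1% and r of 2 to 3, mean follow-up cost would be understated by about 0.5% to 2%. A visible effect on a between-cluster ratio, such as 1.04 to 1.12 masked as 1.00, needs removal rates as unequal as 1% and 5%. All of these inputs are assumptions, and the effect is probably small. The reason to act is that the defect is clear and cheap to remove before the Phase 2 data are extracted.

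**What to change.** 1. In section 4.2, for Phase 2, define active COPD by a Read code on or before the index date plus medication in the year before the index date. This is the window the rule already has in Phase 1 for patients indexed at last data collection. No post-index month then decides this exclusion.
2. State which medications count. If the list includes the asthma drugs used for inclusion, say openly that every patient with a prior COPD code is excluded.
3. Reconcile section 3.2 with sections 5.4 and 6.7 on the year in which service use and costs are measured.
4. For the other listed conditions, run Phase 2 with exclusions limited to codes on or before index and again with codes at any time. Name one as the main analysis and the other as a sensitivity analysis, and add it to section 6.9.

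The cost is a few lines of text, a drug list and one further run on data already planned. The downside is that a few patients later relabelled with another lung disease may remain in one of the two analyses. Comparing the runs shows whether that matters.

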5.0 Study variables and study outcome definitions

5.1 Describing demographic and clinical variables

The demographic and clinical characteristics of interest at index date are: gender, age, smoking status, most recent recorded BMI prior to index date, most recent spirometry recorded prior to index date (PEF, FEV₁, FEV₁/FVC ratio), number with severe asthma, GINA step, Risk Domain Asthma Control and Overall Asthma Control, asthma medications in the year prior to index date, blood eosinophil count.

- Smoking status will be categorised as: never smoked; ex-smoker; or current smoker based on the latest recorded Read code prior to the index date.
- Body Mass Index (BMI) will be calculated from height and weight data if available (weight in kg/height in m²) or taken from the practice recorded BMI value if not.
- The most recently recorded Peak Expiratory Flow (PEF), Forced Expiratory Flow in one second (FEV₁) and Forced Vital Capacity (FVC) will be taken from the practice recorded value. FEV₁/FVC ratio will be calculated using the last recorded of each of these two values. FEV₁% predicted will also be calculated and reported,
- Severe asthma will be defined according to the ERS/ATS guidelines (Chung, Kian Fan, et al. "International ERS/ATS guidelines on definition, evaluation and treatment of severe asthma." European Respiratory Journal (2013): erj02020-2013).
- We will also report the number of patients meeting the definition of severe asthma used in Regeneron RCTs.
- GINA step will be determined by prescribed medication: see Appendix 4. Highest GINA step (1-5) in the year prior to the index date will be reported.
- Risk Domain Asthma Control (RDAC). Controlled asthma will be defined as the absence of the following in the year prior to the index date: (i) an asthma-related A&E attendance, in-patient admission or out-patient department attendance; (ii) an acute course of oral corticosteroids with evidence of a lower respiratory consultation; and (iii) an antibiotic prescribed with evidence of a lower respiratory consultation.

- Overall Asthma Control. Controlled asthma will be defined as the absence of the following aspects of asthma risk during the baseline year: attainment of RDAC and an average daily dose of ≤ 200 mcg salbutamol / ≤ 500 mcg terbutaline.
- The asthma medications of interest are: ICS, ICS/LABA, SABA, SAMA, LABA, LAMA, LABA/LAMA, LTRA, biologics (where known), and chronic oral corticosteroids (see Appendix 5 for algorithm to distinguish between acute and chronic oral corticosteroid prescribing).

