13.7 Appendix 7: Mock table for demographic and clinical variables at index date

	Number of patients
Number of patients eligible for inclusion, n	x
Age (years), mean (SD)	x (x)
Age (years), median (IQR)	x (x)
Male gender, n (%)	x (x)
BMI (kg/m²), n (%)	x (x)
Non-missing	x (x)
Underweight	x (x)
Normal	x (x)
Overweight	x (x)
Obese	x (x)
Mean (SD)	x (x)
Median (IQR)	x (x)
Smoking status, n (%)	x (x)
Non-missing	x (x)
Non-smoker	x (x)
Current smoker	x (x)
Ex-smoker	x (x)
%predicted PEF	
Non-missing, n (%)	x (x)
Mean (SD)	x (x)
%predicted FEV₁	
Non-missing, n (%)	x (x)
Mean (SD)	x (x)
FEV1/FVC ratio	
Non-missing, n (%)	x (x)
Mean (SD)	x (x)
Severe asthma - ERS/ATS definition, n (%)	x(x)
Severe asthma – Regeneron RCT definition, n (%)	x(x)
GINA step	
Non-missing, n (%)	x (x)
Step 1, n(%)	x (x)
Step 2, n(%)	x (x)
Step 3, n(%)	x (x)
Step 4, n(%)	x (x)
Step 5, n(%)	x (x)
Risk Domain Asthma Control, n (%)	x (x)
Overall Asthma Control, n (%)	x (x)
Medication pre-index	x (x)
SABA, n (%)	x (x)
SAMA, n (%)	x (x)
SABA/SAMA, n (%)	x (x)
LABA, n (%)	x (x)
LAMA, n (%)	x (x)
LABA/LAMA, n (%)	x (x)
ICS/LABA, n (%)	x (x)
ICS, n (%)	x (x)
Biologics (where known), n (%)	x (x)
Chronic OCS, n (%)	x (x)
Antibiotics, n (%)	x (x)

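### Section 5.1 derives FEV1/FVC from a last FEV1 and a last FVC chosen separately, with no requirement that they share a date

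*Protocol*

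**What the plan says.** Protocol Section 5.1 lists the ratio among the baseline characteristics, under "most recent spirometry recorded prior to index date". The bullet that defines the variables then works value by value. It takes the latest PEF, FEV1 and FVC ("Forced Vital Capacity (FVC) will be taken from the practice recorded value"), and the FEV1/FVC ratio is to be "calculated using the last recorded of each of these two values".

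The protocol does not require the two values to share a date or a test session. It sets no maximum gap between them and no limit on how far back either may lie. It does not provide for using a ratio that the practice itself recorded.

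The ratio appears once more, in the mock baseline table (Appendix 7). There the row "FEV1/FVC ratio" has a non-missing count and a mean (SD), in a single column for all eligible patients. Section 4.2 states no age limit, and the GINA table in Appendix 4 has separate entries for adults and children.

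**The concern.** FEV1/FVC describes one forced expiration or one test session. Dividing an FEV1 from one day by an FVC from another gives a number that belongs to no test. The data are routine longitudinal practice records, so nothing guarantees that the last FEV1 and the last FVC were recorded together. Asthma is variable, so FVC cannot be presumed equal on the two dates. In children FVC also grows, which gives the error a direction.

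What is at stake is the accuracy of a reported baseline measure of airflow obstruction: its spread, its individual values (some of which could be impossible) and, where children are involved, possibly its level.

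**Working it through.** The protocol gives no figure to reproduce here, so the check is algebra followed by an illustration under stated assumptions.

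**Algebra.** Let FEV1 come from date A and FVC from date B.

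Derived ratio = FEV1(A) / FVC(B) = [FEV1(A) / FVC(A)] × [FVC(A) / FVC(B)] = true ratio at A × k, where k = FVC(A) / FVC(B).

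The derived ratio is right only if k = 1. A same-date pair makes k = 1 by construction.

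| k | true 0.70 becomes | true 0.80 becomes |
|---|---|---|
| 0.9 | 0.63 | 0.72 |
| 1.1 | 0.77 | 0.88 |
| 1.25 | 0.875 | 1.00 |
| 1.5 | 1.05 | 1.20 |

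**Growing child.** Assume that FVC grows 7% a year (not in the protocol) and that the true ratio is 0.85.
- FVC one year older than FEV1: 0.85 × 1.07 = 0.91.
- FVC two years older: 0.85 × 1.07² = 0.85 × 1.1449 = 0.973.
- Reverse case, FEV1 two years older than FVC: 0.85 / 1.1449 = 0.74.

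**Effect on the planned summary.** Inputs, all assumed because the protocol gives none:
- true ratio normal with mean 0.75 and SD 0.10, held between 0.3 and 1;
- log k normal with mean 0 and SD 0.05, 0.10 or 0.15, so changes in FVC have no systematic direction;
- share of patients with different dates 5%, 20% or 50%.

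Simulating 400,000 patients per setting gives, at the two ends of the share range:

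| SD of log k | share mixed | mean, true → derived | SD, true → derived | above 1 among mixed |
|---|---|---|---|---|
| 0.05 | 5% | 0.7495 → 0.7496 | 0.0992 → 0.0996 | 1.0% |
| 0.05 | 50% | 0.7495 → 0.7500 | 0.0992 → 0.1028 | 1.0% |
| 0.10 | 5% | 0.7499 → 0.7501 | 0.0993 → 0.1008 | 3.2% |
| 0.10 | 50% | 0.7499 → 0.7518 | 0.0993 → 0.1132 | 3.3% |
| 0.15 | 5% | 0.7498 → 0.7503 | 0.0996 → 0.1030 | 7.1% |
| 0.15 | 50% | 0.7498 → 0.7543 | 0.0996 → 0.1291 | 6.7% |

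The 20% settings lie between these.

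Hand check of the last row:
- Among mixed patients the mean is 0.7498 × exp(0.15²/2) = 0.7498 × 1.0113 = 0.7583. The overall mean is (0.7498 + 0.7583)/2 = 0.754.
- The second moment is (0.7498² + 0.0996²) = 0.5721 for true ratios and 0.5721 × exp(2 × 0.15²) = 0.5985 for mixed ones, averaging 0.5853.
- SD = √(0.5853 − 0.7541²) = 0.129, as simulated.

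The largest shift in the mean is 0.7543 − 0.7498 = 0.0045. The largest SD is 0.129.

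The small shift in the mean depends on changes that roughly cancel. If, for example, 5% of all patients were children in the two-year case above, the mean would rise by 0.05 × (0.973 − 0.85) = 0.006.

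**The case against.** The strongest counter-reading is that the opening list speaks of the latest spirometry, which suggests a single test, and that date-matching and range checks are programming details often left to a SAP. The first part does not rescue the rule. The sentence that defines the calculation selects each value separately, and a programmer who followed it would pair across dates. If one session was intended, the sentence misstates the intention. Nor is this an omitted detail: the protocol states a derivation rule, and the rule is wrong for mixed-date patients whose FVC changed.

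The objections on weight do stand. The ratio is not in the objectives, is not a resource-use or cost outcome, is not a named confounder, and drives no sample size. The share of mixed-date patients is unknown, so every study-level figure above is conditional. The error also has no fixed direction: an older FEV1 with a newer FVC biases a child's ratio downward.

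Two stronger readings are tempting, and the documents support neither.
- A reader might infer that many patients will be misclassified as obstructed or not. At an illustrative cut of 0.70, about 10% to 24% of mixed-date patients in the simulation fall on the wrong side (0.5% to 12% of all patients). But the protocol applies no threshold to FEV1/FVC, so this misclassification would not appear in any table it specifies.
- A reader might infer that comparisons between comorbidity clusters are biased. Section 6.6 compares demography and asthma severity across clusters without naming this ratio, and leaves the Phase 2 tables to be settled later. Bias would also require the mismatch, or its direction, to differ by cluster, and nothing in the protocol shows that. The two severe-asthma definitions are cited but not reproduced, so no claim is made about whether the ratio enters them.

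**Conclusion.** The point holds as a faulty derivation rule with a limited effect. For any patient whose last FEV1 and last FVC have different dates, the derived ratio is off by the factor by which FVC changed, and it is correct only if FVC did not change. In growing children an older FVC pushes it upward.

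With 5% to 50% mixed dates and undirected FVC changes of log-SD 0.05 to 0.15 (all assumed), the overall mean moves by less than 0.005. The reported SD rises from about 0.10 to at most about 0.13, and roughly 1% to 7% of mixed-date patients get an impossible ratio above 1. No primary objective or sample size is affected. It is worth correcting because the SD is a planned output and the correction is simple.

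**What to change.** Replace the sentence in Section 5.1 with: *FEV1/FVC will be calculated from the most recent FEV1 and FVC recorded on the same date before the index date (or the recorded ratio from that session); otherwise it is missing.* Report the number of patients with a valid pair.

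The work is one sentence and a date match in the code. The real cost is more missing ratios. How many depends on how often practices record both values on one day, which the protocol does not say, so the loss cannot be estimated from it. The 'Non-missing' row already in Appendix 7 will show it. The change concerns variable derivation only.

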4.0 Study population

4.1 Data sources

Phase 1: The Optimum Patient Care Research Database (OPCRD)

- Contains anonymous, longitudinal medical records for 5.3 million patients from about 700 primary care practices across the UK.
- Includes patient-level diagnostic, clinical and prescribing information.

Phase 2: The OPCRD and the Clinical Practice Research Datalink (CPRD).

- The CPRD includes linked primary and secondary care (HES) data for approximately 300 UK primary care practices.
- The HES records from the CPRD are required to identify secondary care service use and costs, and for some measures of disease severity.

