6.0 Statistical analysis

6.1 Sample size

Phase 1: Approximately 220000 OPCRDR patients with active asthma will be available for inclusion in this phase. Of these, approximately 85000 have moderate to severe asthma (GINA steps 4 & 5).

Phase 2: Approximately 220000 OPCRDR patients and 440000 CPRDR patients with active asthma will be available for inclusion in this phase (85000 moderate to severe from OPCRDR and 170000 moderate to severe from CPRDR). Approximately 260000 of the CPRDR patients will have linked secondary care data (HES): the HES records are required to identify secondary care service use and costs, and for some measures of disease severity.

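### Section 5.1 states Overall Asthma Control backwards, and RDAC rests on hospital events that need HES data most patients do not have

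*Protocol*

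**What the plan says.** Section 5.1 defines two control variables, one after the other.

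- **RDAC.** The stem is "Controlled asthma will be defined as the absence of the following in the year prior to the index date", followed by three adverse events. Component (i) is "an asthma-related A&E attendance, in-patient admission or out-patient department attendance". Component (ii) is "an acute course of oral corticosteroids with evidence of a lower respiratory consultation". Component (iii) is an antibiotic prescription with the same kind of consultation.
- **Overall Asthma Control.** The stem is again an absence, but the items are different: "absence of the following aspects of asthma risk during the baseline year: attainment of RDAC and an average daily dose of" reliever, where the ceiling on that dose is set at "≤ 200 mcg salbutamol / ≤ 500 mcg terbutaline".

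Both variables are index-date characteristics. Section 6.4 tabulates these in Phase 1 and plans a similar set of outputs in Phase 2. The mock table in Appendix 7 has a line for each.

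On data sources, Section 4.1 assigns Phase 1 to the OPCRD alone, described as primary care records: "Includes patient-level diagnostic, clinical and prescribing information". Phase 2 adds the CPRD, and the section says: "The HES records from the CPRD are required to identify secondary care service use and costs, and for some measures of disease severity". Section 6.1 gives about 220,000 OPCRD and 440,000 CPRD patients, and states: "Approximately 260000 of the CPRDR patients will have linked secondary care data (HES").

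Sections 5.4 and 6.7 limit secondary care resource use and costs to linked patients or practices. Section 6.4 reduces the Phase 1 reporting of comorbidity activity and severity because HES is absent. Nothing comparable is said about RDAC or Overall Control.

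**The concern.** There are two separate problems, of unequal certainty.

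The first is logical. For RDAC, absence is the right word because the listed items are bad outcomes. For Overall Control the same stem is placed in front of good outcomes: attaining RDAC, and reliever use at or below a ceiling. Taken as written, the rule turns the variable round. Anyone programming from the protocol must either follow the text and get the wrong answer or depart from it without authority.

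The second is about ascertainment. RDAC treats no recorded hospital event as no hospital event. Where HES is not linked, a hospital event that never reached the GP record looks the same as one that did not happen, and the patient can be counted as controlled. The error can run only in that direction. In Phase 2 it would also make the meaning of the variable depend on whether a patient is linked. A difference in control between linked and unlinked patients, or between OPCRD and CPRD, could then be partly an artefact of data source. Overall Control inherits the problem because RDAC is one of its two conditions.

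**Working it through.** **Step 1: the Overall Control rule.** Let A be RDAC attained and B be average daily reliever dose at or below the stated limits. The evident intent is that controlled means A and B. The wording, absence of A and B, can be read as not both or as neither.

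| A | B | Evident intent | Literal: not both | Literal: neither |
|---|---|---|---|---|
| yes | yes | controlled | uncontrolled | uncontrolled |
| yes | no | uncontrolled | controlled | uncontrolled |
| no | yes | uncontrolled | controlled | uncontrolled |
| no | no | uncontrolled | controlled | controlled |

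Read as not both, all four cells are wrong. Read as neither, two cells are wrong, and they are the two extremes: the best-controlled patients are called uncontrolled and the worst are called controlled. Neither reading gives the intended group. Appendix 7 carries only the variable name, so it does not settle the matter.

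**Step 2: patients without HES.** The inputs are the counts in Section 6.1. They are treated as non-overlapping across databases, which the protocol does not state.

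- Phase 1: 220,000 / 220,000 = 100%.
- Phase 2 total: 220,000 + 440,000 = 660,000.
- Phase 2 without HES: 660,000 − 260,000 = 400,000, and 400,000 / 660,000 = 60.6%. This is 220,000 from the OPCRD plus 180,000 from the CPRD (180,000 / 440,000 = 40.9% of CPRD).
- Phase 2 with HES: 260,000 / 660,000 = 39.4%.

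These are the patients in whom component (i) could be under-recorded. They are not the patients misclassified.

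**Step 3: how large the bias could be.** An unlinked patient is wrongly counted as RDAC-controlled only if three things hold together: a qualifying hospital event occurred, neither component (ii) nor (iii) was met, and the event is not in the GP record. So

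excess controlled = h × q × m,

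where h is the share of patients with a hospital event, q the share of those with neither (ii) nor (iii), and m the share of those whose event is missing from the GP record. The documents give none of the three. The ranges below are assumptions, for illustration only: h 2–10%, q 10–50%, m 25–100%.

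| | h × q × m | Phase 1 | Phase 2, if sources are pooled |
|---|---|---|---|
| Lowest | 0.02 × 0.10 × 0.25 = 0.0005 | 0.05 points; 220,000 × 0.0005 = 110 patients | 400,000 × 0.0005 = 200 patients; 200 / 660,000 = 0.03 points |
| Highest | 0.10 × 0.50 × 1.00 = 0.05 | 5.0 points; 220,000 × 0.05 = 11,000 patients | 400,000 × 0.05 = 20,000 patients; 20,000 / 660,000 = 3.0 points |

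The range spans two orders of magnitude. The direction is known; the size is not. Under the corrected Overall Control rule, the excess in that variable cannot exceed the excess in RDAC, because a low reliever dose is also required.

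**The case against.** **The reversal is a slip whose intent is plain.** The stem was evidently carried over from the RDAC item above it. Words such as attainment, and a ceiling on dose, can only describe control, so a sensible programmer would code it correctly. This is probably true, and it lowers the chance of harm. It does not remove the need to correct the only operative definition of a variable reported in both phases.

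**GP records may hold hospital events.** The OPCRD contains diagnostic and clinical information. The literature review in Appendix 14, writing about anaphylaxis, expects the main diagnosis of a hospital-treated event to be what reaches the GP record. A reader might infer that every unlinked patient passes component (i) automatically. The documents do not support that. Some events will be coded in primary care, and some patients will fail on (ii) or (iii) anyway. Under-recording is plausible; its extent is not shown.

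**The protocol already recognises the HES limitation.** A reader might infer that only costs are confined to linked patients. In fact Sections 5.4 and 6.7 confine secondary care resource use as well, and Section 4.1 mentions some measures of disease severity. What stands is that RDAC, which uses the same kind of event, gets no restriction, label or named source. A SAP could supply the code source. The inconsistency, however, lies in the protocol's own text.

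**Control is peripheral.** A reader might infer that control is an outcome or covariate in the Phase 2 models, or a characteristic of each cluster. Section 6.6 does not list it among the cluster characteristics, and Section 5.1 defines severe asthma and GINA step separately. Appendix 12, the cluster resource-use table, omits it. This objection stands, and it limits the point to the descriptive control variables.

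**Pooling is not stated.** Section 4.1 names both databases for Phase 2 without saying that they are merged. The pooled figures above are therefore conditional. The gap in ascertainment exists either way, since the CPRD itself contains linked and unlinked patients.

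**Conclusion.** The definition of Overall Asthma Control is wrong as written and must be corrected before programming. This rests on the text alone and needs no assumption.

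The RDAC part holds in a more limited form. A hospital-event component is reported for all of Phase 1 and about 61% of Phase 2 without the data source that the protocol says is required, and with no restriction or label. The 61% assumes no overlap between the OPCRD and the CPRD. Any resulting bias is towards control and falls only on unlinked patients. No rate in the documents fixes its size. On the assumed inputs it runs from 0.05 to 5.0 percentage points in Phase 1, and from 0.03 to 3.0 points in a pooled Phase 2, so it may be negligible. A claim that control is overstated by a substantial and known amount would go beyond the documents.

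The frequency and ranking of comorbidity clusters, the Phase 1 primary objective, are not affected. What is affected is the description of asthma control in both phases.

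**What to change.** 1. In Section 5.1, replace the Overall Control sentence with: *Overall control = RDAC attained AND average daily reliever dose at or below the limits already stated.* The limits themselves are left as they are. The cost is one sentence.
2. Report full RDAC and full Overall Control in the approximately 260,000 HES-linked patients.
3. In all other patients, including the whole of Phase 1, report a separately named version built from primary care records, and state which records feed it.
4. Report that primary-care version in the HES-linked patients as well. The difference between the two versions in the same people measures the bias that cannot be sized today.

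The cost of items 2 to 4 is a few sentences, one extra tabulated variable, and no full RDAC or full Overall Control in Phase 1. If the sponsor prefers one variable throughout, the least that is needed is a statement that component (i) uses GP-recorded contacts where HES is absent, with a footnote on each table. That is cheaper, but it leaves the difference between sources unmeasured.
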